2. SYNOPSIS

Study Identifier	The HER Project	
Study Title	The HER Project: Homologous Recombination Deficiency in EGFR-Mutated NSCLC, a retrospective and prospective translational single-center study	
Protocol Version and Date	Ver 1.0 – 30/SEP/2025	
Sponsor	IRCCS Ospedale San Raffaele [name]	
Co-Sponsor	N/A	
Funding Source(s)	Medical Oncology internal Funding (Eredità [name])	
Principal Investigator	[name] Medical Oncologist IRCCS Ospedale San Raffaele	
Study Description	The study aims to evaluate the prevalence of homologous recombination deficiency (HRD) in metastatic EGFR-mutated NSCLC and to assess its correlation with clinical and molecular features. Based on the hypothesis that HRD identifies a distinct EGFRm subgroup with prognostic value and a potential sensitivity to PARP inhibitor-based strategies, translational analysis will be performed with multiple pre-clinical models, ranging from human cancer cells to murine models.	
Study Design	Observational, retrospective and prospective single-center study	
Primary Objective To evaluate prevalence of HRD in our internal cohort of metastatic EGFRm NSCLC	Primary Endpoint Proportion of EGFRm NSCLC with an HRD positive score evaluated by AmoyDx HRD Panel or similar (GSS \geq 50).	Time point(s) At T0 on baseline tumour samples
Secondary Objectives To assess correlations between HRD score (pos/neg) and: 
- Clinical variables (PFS, OS, metastatic sites)- Molecular events (type of EGFR mutations, VAF, drug resistance mechanisms i.e. gene amplification)	Secondary Endpoints Overall survival (OS), Progression-free survival (PFS), tumour genomic mutations.	Time point(s) At T0 on baseline tumour samples
Exploratory Objectives 
- To assess the efficacy of osimertinib and olaparib combination in TKI-naïve EGFRm NSCLC cell lines (HCC-4006, HCC-827, and HCC-2935, ranging from low to high HRD score);- To test the drug combination in patient-derived models of EGFRm tumours (PBMCs, organoids, and PDXs);	Tumor growth, cellular viability, drug toxicity.	N/A

 - To rule out toxicity the drug combination and assess treatment response, thanks to our immune competent GEMM model of EGFRm16 and TP53 wt/null. 		
Study Population	Adult patients (≥ 18 years) with metastatic EGFR-mutated non-small cell lung cancer (NSCLC) eligible for treatment with EGFR-TKI according to standard clinical practice, with available tumor tissue suitable for HRD testing.	
Inclusion Criteria	
The population of interest will include patients affected by EGFR-mutated NSCLC. Individuals must meet all the following inclusion criteria in order to be eligible to participate in the study:
 
 1. Participant is willing and able to give informed consent for participation in the study. However, concerning the retrospective cohort, the large sample sizes needed and considering that the disease involved in this study affects elderly subjects with co-morbidities and presents a significant mortality rate based on the stage of the disease, deceased and untraceable patients will also be included. 2. Age ≥ 18 years old 3. Have a metastatic histologically confirmed NSCLC 4. Presence of EGFR common mutations (i.e. ex19del and L858R) 5. Patients treated in first-line setting with 4th generation EGFR-TKI inhibitors (i.e. osimertinib, lazertinib) or beyond 6. Have archival tumor tissue suitable for HRD testing with AmoyDx Focus panel or similar 7. Survival follow-up available (for retrospective cohort) 	
Exclusion Criteria	
All individuals meeting any of the following exclusion criteria at baseline will be excluded from the study participation:
 
 1. Insufficient baseline tumour tissue (unsuitable for HRD scoring) 2. Presence of EGFR uncommon mutations (i.e. ex20ins) 3. Known presence of co-occurring uncommon EGFRm, ALK, ROS1, or oncogenic drivers. 	
STUDY OBJECT		
DRUG		
Sample Size	N= 100 Total sample size (N=50 retrospective cohort; N=50 prospective cohort)	
Statistical Design	
According to the literature, to obtain an adequate number of patients to allow subgroup analyses and explore clinical and molecular correlations, we calculated a sample size of 100 patients (50 retrospective; 50 prospective) to conduct an exploratory proof-of-concept study, in which we expect to observe around 25 HRD-positive cases (the precision of the estimate corresponds to a 95% confidence interval with a half-width of approximately 8.5 percentage points, which is considered clinically relevant). Based on the historical caseload at IRCCS Ospedale San Raffaele (≈ 15 eligible patients/year), recruiting the planned sample over 4 years is feasible. For the retrospective cohort, we estimate that $\approx 30\%$ of patients have insufficient residual archival tumor tissue, therefore the planned 50 patients will be included considering a longer interval (1/1/2020 - 30/09/2025).
 
For the Primary and Secondary Objectives, continuous variables will be summarized using mean, median, range, and standard deviation. Categorical variables will be described using frequency and percentage. To test association between categorical variables, chi-squared test will be applied. To compare survivals between groups (i.e. HRD positive vs negative, cut-offs to be explored) log-rank test will be applied. Time-to-event outcomes will be represented using Kaplan-Meier curves.
	

	
For the Exploratory Objectives, parametric and non-parametric analyses will be used to compare differences in cell lines and phenotypes between groups. For the in vivo studies, differences in tumour size and phenotype will be evaluated at different timepoints and compared with t-test. For all statistical tests, $p < 0.05$ will be considered statistically significant.
	
Duration of the Study	
Duration of enrolment: 4 years, starting from ethical approval
 
Duration of total study period: 7 years, including 4 years of enrolment and 3 years of follow-up (01/01/2026-31/12/2032). Based on historical caseload at IRCCS Ospedale San Raffaele, we estimate an average of ≈ 15 EGFR^m metastatic NSCLC patients eligible per year.
 
Retrospective data collection will include patients respecting the eligibility criteria from 1/1/2020 to 30/09/2025.
	

3. ABBREVIATIONS AND DEFINITIONS

3.1. Abbreviations

AE	Adverse event
CRF	Case Report Form
CRO	Contract Research Organization
CTC	Clinical Trial Center
DPIA	Data Protection Impact Assessment
EC	Ethics Committee
EGFR	Epidermal Growth Factor Receptor
GCP	Good Clinical Practice
GSS	Genomic Scarring Score
HRD	Homologous Recombination Deficiency
ICF	Informed Consent Form
ICH	International Conference on Harmonization
NSCLC	Non-small cell lung cancer
OS	Overall Survival
OSR	Ospedale San Raffaele
PARP inhibitors	Poly (ADP-ribose) polymerase inhibitors
PDX	Patient-derived xenograft
PFS	Progression-Free Survival
PI	Principal Investigator
SOP	Standard Operating Procedure
TKI	Tyrosine Kinase Inhibitor

3.2. Definitions

AmoyDx® HRD Focus Panel	A homologous recombination deficiency (HRD) test designed to simultaneously detect genetic aberrations of BRCA1 and BRCA2 genes and HRD status [0].
-------------------------	---

GSS	A machine learning-based model which assesses genomic instability by analyzing different types of copy number events across the genome [0]. It can be calculated as the sum of the events of loss of heterozygosity (LOH), large-scale state transition (LST) and telomere allele imbalance (TAI) [20].
HRD	A condition linked to an impaired DNA repair mechanism that contributes to genomic instability.
PDX	A type of cancer model in which tumour tissues or cells from patients are implanted into immunodeficient or humanized mice.

4. BACKGROUND AND RATIONALE

Introduction

Lung cancer is the most common diagnosed cancer, with almost 2.5 million new cases per year, and the leading cause of cancer-related death (18.7%), according to GLOBOCAN (2022) [1,2]. Non-small cell lung cancer (NSCLC) is the most prevalent subtype, accounting for 85% of lung cancers [2]. Epidermal growth factor receptor (EGFR) is a transmembrane tyrosine kinase receptor that regulates survival, proliferation and differentiation in mammalian cells [3]. EGFR mutations occur in around 30% of patients affected by NSCLC, representing the second most frequent targetable oncogenic driver in NSCLC [4,5].

The treatment landscape for metastatic EGFR-mutated (EGFRm) NSCLC has significantly evolved since the introduction of 1st generation tyrosine kinase inhibitors (TKIs) in 2010. While osimertinib (a 3rd generation TKI) is currently the standard first-line treatment worldwide in the advanced setting, emerging combination strategies, such as osimertinib plus chemotherapy (FLAURA2 trial) [6] or lazertinib plus amivantamab (MARIPOSA trial) [7], improved progression-free survival (PFS) and overall survival (OS) compared to TKI alone. However, these drug combinations often cause increased treatment-related toxicities, impacting both patients' quality of life and healthcare costs [8]. For this reason, it becomes crucial to identify predictive biomarkers to guide patient selection for combination therapies. For example, post-hoc analyses of FLAURA2 were conducted on poor-risk populations, such as EGFRm patients with high tumour burden or TP53 co-mutations [9,10]. Despite better outcomes of chemotherapy plus osimertinib across all patient subgroups, only 1 out of 4 patients had baseline tissue samples available for wider genome sequencing. Therefore, understanding the role of co-alterations in EGFRm tumours remains to be explored, particularly those associated with shorter OS and/or more aggressive clinical presentations.

Targeting HRD pathway with PARP-inhibitors in Non-small cell lung cancer

Homologous recombination deficiency (HRD) is a condition linked to an impaired DNA repair mechanism that contributes to genomic instability in several cancers, including NSCLC. PARP-inhibitors (PARPi), drugs targeting a key protein involved in DNA repair, are already available in clinical practice for the treatment of other HRD-positive subgroups of solid tumours (e.g. breast, ovarian, prostate cancer) [11]. In NSCLC, however, their clinical benefit remains unclear. Previous studies evaluating PARPi in NSCLC, including combinations with chemotherapy or immunotherapy, have shown modest or non-significant improvements in PFS and OS [12, 13, 14, 15, 16]. However, a significant limitation of these studies is the lack of HRD status assessment, which may have diluted the expected benefits in HRD-positive patients.

Interestingly, emerging evidence suggests that a higher Genomic Scarring Score (GSS), a surrogate for HRD, may predict PARPi sensitivity better than the traditional assessment of the mutational status of homologous recombination repair (HRR) genes [17]. In this study, the administration of PARPi significantly delayed tumour growth in patient-derived xenograft (PDXs) with high GSS, half of which carried pathogenic/likely pathogenic somatic HRR mutations [17]. Importantly, favourable responses to the PARPi-olaparib were observed regardless of HRR gene mutation status, underscoring the potential of GSS as a robust biomarker to more effectively select patients for PARPi-based therapies [17].

HRD in EGFR mutated NSCLC

In a Chinese cohort of HRD-positive NSCLC, EGFR-mutated tumours are associated with poor TKI response [18], which might be explained by gene amplifications like MET, a common resistance mechanism that can be promoted by HRD [19]. Studies also showed the co-occurrence of biallelic TP53 mutations and high HRD score in poor-risk EGFRm NSCLC, suggesting a link between this tumour genotype and TKI-resistance [20]. In preclinical models of NSCLC, osimertinib-resistant EGFRm cell lines exhibited sensitivity to olaparib, leading to increased DNA damage and cell death via a pro-oxidant state. Moreover, combining osimertinib with a PARPi *in vivo* significantly improved tumour regression compared to osimertinib alone [21]. Altogether, these findings lead to hypothesize that the HRD positive score/GSS may define a patient subgroup that could benefit from PARPi-based combination therapy.

Clinical trials evaluating EGFR-TKIs with PARPi failed to achieve their primary endpoint of PFS, possibly due to a lack of patient selection based on HRD score or other molecular criteria [22]. However, subsequent analyses of the GOAL trial found a stronger synergy between gefitinib (a 1st generation TKI) and olaparib in tumours with higher

BRCA1 expression [23], supporting a predictive role for targeting DNA damage repair pathways. In operable NSCLCs, the percentage of HRD positive tumours is ~20-30% [24], suggesting that the acquisition of HRD status could be an early event. Importantly, a similar incidence was observed in a Chinese cohort of any-stage EGFRm or ALK-rearranged NSCLC patients in which the cases with high HRD score are ~33% of the total [18]. The sensitivity of EGFRm tumours to platinum-based doublets [25], which is a known characteristic of HRD-positive tumours, and a larger compendium evidence of chromosomal instability further support exploring the role of HRD in EGFR-mutated lung cancer, paving the way for new targeted therapeutic approaches [26].

The HER Project

With the HER project, we will investigate the role of HRD and genomic instability (GSS) in EGFRm NSCLC by i) defining the fraction of metastatic EGFRm tumours with HRD positive score, ii) correlating HRD score with patient outcomes, and iii) assessing the synergic efficacy of EGFR-TKIs plus PARPi based on the HRD score in different preclinical settings, ranging from cell lines to a murine model of spontaneous EGFRm lung cancer. We expect that this drug combination will be effective in a specific subset of EGFR tumors. However, even if we won't observe any relevant findings by targeting this pathway, our work will increase our knowledge about DNA damage repair and drug resistance in EGFRm tumours.

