5. OBJECTIVES AND ENDPOINTS

Objectives	Endpoints	Time point(s)
Primary Objective To evaluate prevalence of HRD in our internal cohort of metastatic EGFRm NSCLC	Primary Endpoint Proportion of EGFRm NSCLC with an HRD positive score evaluated by AmoyDx HRD Panel or similar (GSS \geq 50).	At T0 on baseline tumour samples
Secondary Objectives To assess correlations between HRD score (pos/neg) and: 
 - Clinical variables (PFS, OS, metastatic sites) - Molecular events (type of EGFR mutations, VAF, drug resistance mechanisms i.e. gene amplification) 	Secondary Endpoints Overall survival (OS), Progression-free survival (PFS), tumour genomic mutations.	At T0 on baseline tumour samples
Exploratory Objectives 
 - To assess the efficacy of osimertinib and olaparib combination in TKI-naïve EGFRm NSCLC cell lines (HCC-4006, HCC-827, and HCC-2935, ranging from low to high HRD score); - To test the drug combination in patient-derived models of EGFRm tumours (PBMCs, organoids, and PDXs); 	Tumor growth, cellular viability, drug toxicity.	N/A

- To rule out toxicity the drug combination and assess treatment response, thanks to our immune competent GEMM model of EGFRm16 and TP53 wt/null.

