14. STATISTICS

14.1. Description of Statistical Methods

The statistical analysis will address the primary, secondary, and exploratory objectives of the study. For descriptive statistics, continuous variables will be summarized using mean, median, range, and standard deviation, while categorical variables will be described using frequency and percentage. Comparisons between groups (e.g., HRD positive vs HRD negative) and time-to-event analyses will be performed with appropriate statistical tests, as detailed in Section 14.4. Statistical significance will be set at a two-sided p-value < 0.05. Analyses will be performed through statistical software such as Microsoft Excel, R, and SPSS.

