14.4 Statistical Design

For the Primary and Secondary Objectives, continuous variables will be summarized using mean, median, range, and standard deviation. Categorical variables will be described using frequency and percentage. To test association between categorical variables, chi-squared test will be applied. To compare survivals between groups (i.e. HRD positive vs negative, cut-offs to be explored) log-rank test will be applied. Time-to-event outcomes will be represented using Kaplan-Meier curves.

For the Exploratory Objectives, parametric and non-parametric analyses will be used to compare differences in cell lines and phenotypes between groups. For the *in vivo* studies, differences in tumour size and phenotype will be evaluated at different timepoints and compared with t-test. For all statistical tests, $p < 0.05$ will be considered statistically significant.

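### The preclinical aims of synergy and of excluding toxicity are not answered by the group-difference tests stated in Section 14.4

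*Protocol*

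**What the plan says.** The closing part of Section 4 (The HER Project) sets three aims. The third, which concerns the preclinical models, is "assessing the synergic efficacy of EGFR-TKIs plus PARPi based on the HRD score". The exploratory objectives in Section 5, repeated in the Synopsis, are worded differently. For the cell lines the objective is "To assess the efficacy of osimertinib and olaparib combination in TKI-naïve EGFRm NSCLC cell lines"; for the mouse model it is "To rule out toxicity the drug combination and assess treatment response". The endpoints for all of these are "Tumor growth, cellular viability, drug toxicity".

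Section 14.4 gives the analysis. In general, "parametric and non-parametric analyses will be used to compare differences in cell lines and phenotypes between groups". The animal experiments have a sentence of their own, which fixes the method: "differences in tumour size and phenotype will be evaluated at different timepoints and compared with t-test". On the level, Section 14.1 states: "Statistical significance will be set at a two-sided p-value < 0.05".

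The Protocol names no reference model for the absence of interaction (such as Bliss or Loewe), no combination index, no drug-by-drug or drug-by-HRD contrast, no toxicity margin and no confidence bound on toxicity.

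**The concern.** Three questions are asked, and a plain group comparison answers none of them.

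- **Synergy.** A significant difference between the combination and one drug shows that the other drug adds something. Synergy means that the joint effect exceeds what the two drugs would give if they acted independently, and a purely additive pair also passes the difference test.
- **Dependence on HRD.** A significant result in a high-HRD model beside a non-significant one in a low-HRD model is not a test of the difference between the two models.
- **Absence of toxicity.** Failing to find a difference, or seeing no events, in a small group is compatible with material harm.

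Section 4 connects this work to the hypothesis that an HRD-positive subgroup could benefit from a PARP-inhibitor combination. An unsupported conclusion of synergy, HRD dependence or lack of toxicity would feed that hypothesis. The primary prevalence estimate and the patient-level analyses do not depend on it.

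**Working it through.** The Protocol gives no group size, SD, effect size or margin for the preclinical work, so it has no figure of its own to reproduce on this point. Only the two-sided 0.05 level comes from the document (Section 14.1). Everything else below is assumed and shown over a range.

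**1. Synergy.** Assume that the second drug alone multiplies tumour volume by 0.7 and that the combination is exactly additive on log volume (Bliss independence: the volume ratios multiply). The combination then differs from the first drug by ln(0.7) = −0.357. With d = 0.357/SD, the two-sided t-test has 2n − 2 degrees of freedom and non-centrality d√(n/2). Its probability of significance is:

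| SD of log volume | d | n = 6 per arm | n = 8 | n = 10 |
|---|---|---|---|---|
| 0.3 | 1.19 | 46% | 60% | 71% |
| 0.4 | 0.89 | 29% | 38% | 47% |
| 0.5 | 0.71 | 20% | 26% | 33% |

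There is no synergy in any cell. The t-test is behaving correctly, because the second drug does have an effect. The error arises only if the result is read as synergy.

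Requiring the combination to beat both single agents does not solve this. In 40,000 simulated experiments per setting (control, A, B and A+B; SD 1; exactly additive; single-agent effects of 1 to 2 SD), both t-tests favoured the combination significantly in:

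- 14% to 68% of runs at n = 5 per group;
- 40% to 98% at n = 10;
- 62% to over 99% at n = 15.

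The interaction contrast (A+B) − A − B + control rejected in about 5% throughout, as it should.

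**2. Dependence on HRD.** Assume the same true effect of 1 SD in a high-HRD and a low-HRD model. Each test has power p = 0.35, 0.46 or 0.56 at n = 6, 8 or 10.

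- Exactly one test is significant with probability 2p(1 − p) = 0.455, 0.497 or 0.493.
- It is the high-HRD model alone in half of those cases: p(1 − p) = 0.23, 0.25 or 0.25.

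So a pattern that looks like HRD dependence appears in roughly a quarter of such pairs when there is none.

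**3. Toxicity.**

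- A true harm of 1 SD is non-significant with probability 1 − p = 65%, 54% or 44% at n = 6, 8 or 10. A harm of 0.5 SD is missed in 85% at n = 8 and 82% at n = 10.
- If no event is seen in n animals, the one-sided 95% upper bound on the event rate is 1 − 0.05^(1/n): 45% at n = 5, 31% at n = 8, 26% at n = 10 and 18% at n = 15.
- Excluding a margin of m SD (one-sided 0.025, 80% power, true difference 0) needs about 2(1.96 + 0.84)²/m² animals per group. For m = 1 this is 15.7, so 16; for m = 0.5 it is 62.7, so 63.

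**4. Price of the interaction test.** With n per group, the simple difference has variance 2σ²/n and the interaction contrast 4σ²/n. The standard error is therefore √2 times as large, and the same absolute effect needs twice the animals per group.

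**The case against.** The synergy half rests on one phrase in the Background. Section 5 speaks of efficacy and of testing the combination, Section 8 of assessing it, and no endpoint mentions synergy. Group comparisons suit the objectives in that wording. This stands: the text does not commit the study to demonstrating synergy. What remains is that Sections 4 and 5 state the aim differently, and that the Section 4 version has no matching analysis.

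A reader might infer that, under Section 14.4, additive combinations would be reported as synergic and harmful ones as free of toxicity whenever p exceeds 0.05. The Protocol does not support that. Section 14.4 contains no such decision rule, its t-test is stated for tumour size and phenotype, and it names no test for toxicity. The defect is a gap between aims and methods, not a written rule for a wrong conclusion.

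The general reference to parametric and non-parametric analyses could cover an interaction model, and a statistical analysis plan that is not shown may add one. This stands in part. The sentence confines those analyses to differences between groups, and the in vivo method is fixed as a t-test. The toxicity objective is worded as exclusion in the objectives table itself, which this argument does not reach.

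The magnitudes are also entirely assumed. That is correct, and they serve only as illustration. Finally, Sections 14.2 and 14.5 describe the study as exploratory and mainly descriptive, which limits the weight of the point.

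**Conclusion.** The point holds as a minor mismatch between stated aims and stated analyses, confined to the exploratory preclinical work. The group-difference comparisons in Section 14.4 do not separate synergy from additivity, do not test dependence on HRD and do not exclude toxicity. The first and third statements follow from what the tests compare and need no assumption about group sizes. The second applies if separate results by HRD level are set side by side.

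How often a misleading result would arise cannot be derived from the Protocol. The ranges of 20% to 71% (significant without synergy) and 44% to 65% (1-SD harm missed) rest on an assumed 6 to 10 animals per arm and, for the first range, on an assumed 30% shrinkage and an SD of log volume of 0.3 to 0.5.

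A reader might also infer that adding an HRD interaction term would settle the HRD question. The models described do not support that. Three named cell lines confound HRD level with cell-line identity, and the mouse model is characterised by EGFR and TP53 status with no HRD level stated.

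**What to change.** - **Synergy (Section 14.4).** Where control and both single-agent arms are run, compare the observed combination effect in vitro with a Bliss or Loewe expectation. In vivo, estimate the drug-by-drug interaction on log tumour volume instead of relying on the t-test alone. Where those arms are not run, reword the Section 4 aim to comparing the combination with single agents. Either way, align Sections 4 and 5.
- **HRD.** State that dependence on HRD will be described, not tested, across the three cell lines. Where enough models of differing HRD exist, the term to test is drug-by-drug-by-HRD; an HRD-by-combination term alone would not show that synergy depends on HRD.
- **Toxicity (Section 5 and Synopsis).** Replace the exclusion wording with describing toxicity, with confidence intervals. Keeping a claim of exclusion would need a margin set in advance and possibly more animals, as the 16 and 63 per group above show.

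**Cost.** If the single-agent and control arms are already planned, only wording and analysis change. The downside is lower power for the interaction, so a synergy claim becomes harder to make.
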